9.3.3. Time course efficacy analysis

The time course efficacy analysis uses the sum of modified items 6 and 7 of the TETRAS-PS. At Baseline: items 6 and 7 of the TETRAS-PS will be assessed serially across the day at 6 time

points: predose, 1, 2, 4, 6, and 8 hours post-dose. At Week 8 visit, items 6 and 7 of the TETRAS-PS will be assessed serially at the same 6 time points: predose, 1, 2, 4, 6, and 8 hours post-dose (time matched at Baseline). The 1 hour post-dose assessment at Baseline as well as Week 8 should be taken from the full TETRAS-PS assessment.

The time course efficacy analysis will be performed with a mixed model with repeated measurements (MMRM). The time-matched change on items 6 and 7 of the TETRAS-PS will be the dependent variable in the model. The model will include time-matched baseline TETRAS-PS item 6 and 7, treatment group, time points, treatment group by time point interaction and randomization stratum as fixed effects, and participant as a random effect.

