Baseline	A blinded rater will assess TETRAS-PS (assess at same time of day as the anticipated 1-hour postdose assessment at post-baseline visits)
	[Optional] Assess items 6 and 7 of the TETRAS-PS serially across the day at 6 time points: initial assessment, 1 (use assessment from full TETRAS-PS for this time point), 2, 4, 6, and 8 hours after initial assessment
Week 4	A blinded rater will assess TETRAS-PS 1-hour postdose.
Week 8	A blinded rater will assess TETRAS-PS 1-hour postdose. [Optional] Assess items 6 and 7 of the TETRAS-PS serially across the day at 6 time points: predose, 1 (use assessment from full TETRAS-PS for this time point), 2, 4, 6, and 8 hours postdose (time points should correspond to the same time of day as Baseline assessments).
Week 12	A blinded rater will assess TETRAS-PS 1-hour postdose.
E/D Visit	A blinded rater will assess TETRAS-PS 1-hour postdose (assess at same time of day as 1-hour postdose assessment at post-baseline visits).

Abbreviations: EAC = Eligibility Adjudication Committee; ET = essential tremor; TETRAS-PS = The Essential Tremor Rating Assessment Scale - Performance Subscale.

Note: Potential participants screened an additional time (rescreened) who had previously met the inclusion criterion relative to ET diagnosis confirmed by the central EAC (Inclusion Criterion #2) will not have to complete the TETRAS-PS assessment and subsequent central review by the EAC at Screening Visit 1 or 2, as applicable.

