9.4.4. Tertiary/Exploratory Endpoints

For the analysis of change from Baseline to Weeks 4 and 8 on the TETRAS composite outcome score, TETRAS-ADL, TETRAS-PS, TETRAS upper limb score (item 4), TETRAS total score, the analyses results will be derived from the MMRM used in the Week 12 analysis on the primary estimand and the secondary endpoints.

For the analysis of change from Baseline to Week 12 on modified items 6 and 7 of the TETRAS-PS (where each item is modified from 9 response items [due to 0.5 scoring increments] to 4 response items), the sum of modified items 1 to 11 of the TETRAS-ADL subscale (where each item is modified from 5 response items to 4 response items), and TETRAS total score, the analyses results will be derived from a similar MMRM used in the Week 12 analysis on the primary estimand endpoint.

For the analyses of proportion of participants who improved ≥ 1 point from Baseline to Weeks 4 and 8 on the CGI-S, the CMH test stratified by the randomization stratum will be used for the comparison between each dose of JZP385 and placebo. For the analyses of PGI-C and CGI-C at Weeks 4 and 8, the CMH test stratified by the randomization stratum will be used for the comparison between each dose of JZP385 and placebo.

For the analysis of change in SF-36v2 score from Baseline to Week 12, a descriptive summary at each scheduled visit along with change from Baseline to Week 12 will be tabulated and listed.

The time course efficacy analysis using the sum of modified items 6 and 7 of the TETRAS-PS will be performed with a mixed model. The model will include treatment group, time points, treatment group by time point interaction and the randomization stratum as fixed effects, and participant as a random effect.

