5. STUDY DESIGN

5.1. Summary of Study Design

This is a 12-week, double-blind, placebo-controlled, randomized, parallel-group, multicenter study of the safety and efficacy of JZP385 in the treatment of adult participants with moderate to severe ET.

[figure not shown]
The total duration of the study for each participant will be approximately 19 weeks. During the Screening Period, which will occur over a period of up to 35 days (an additional 28 days are permitted for participants who require washout of primidone), all participants will be evaluated for eligibility and will washout any prohibited medications. Participants eligible for the study will be randomized in a 1:1:1:1 ratio to receive once daily doses of 10, 20, or 30 mg JZP385 or placebo during a 12-week Double-blind Treatment Period. Randomization will be stratified by the TETRAS composite outcome score (≤ 17 or > 17) and the use of concomitant antitremor medication (Yes or No), as assessed at the Baseline Visit. JZP385 will be administered orally (PO) once daily in the morning on an empty stomach for 12 weeks. Dosing will be titrated as follows:

- Participants randomized to the 10 mg/day dose will initially receive 5 mg/day from Day 1 through Day 7, and 10 mg/day starting on Day 8.
- Participants randomized to the 20 mg/day dose will initially receive 5 mg/day from Day 1 through Day 7, 10 mg/day from Day 8 through Day 14, and 20 mg/day starting on Day 15.
- Participants randomized to the 30 mg/day dose will initially receive 5 mg/day from Day 1 through Day 7, 10 mg/day from Day 8 through Day 14, 20 mg/day from Day 15 through Day 21, and 30 mg/day starting on Day 22.

Once participants reach their assigned fixed dose, they will continue on that dose for the remainder of the planned 12-week treatment period. No dose adjustments will be allowed. Participants who cannot tolerate their assigned fixed dose of JZP385 will be withdrawn from the study.

The schema of study is shown in Figure 1.

Figure 1 Study Schema

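### The time-course model's single slope on a time-varying baseline can lose much of the adjustment for participants' overall severity, costing precision (not causing bias) in the dose-versus-placebo contrasts at each time point and over the day

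*SAP*

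**What the plan says.** SAP 9.3.3 defines the outcome: "The time-matched change on items 6 and 7 of the TETRAS-PS will be the dependent variable in the model". On the right-hand side, "The model will include time-matched baseline TETRAS-PS item 6 and 7, treatment group, time points, treatment group by time point interaction", with "randomization stratum as fixed effects, and participant as a random effect". There is no participant-level baseline and no baseline-by-time term.

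Protocol 9.4.4 describes the same analysis without any baseline covariate: "The model will include treatment group, time points, treatment group by time point interaction and the randomization stratum as fixed effects", with participant as a random effect. SAP 7.6, which lists changes to the planned analyses, does not mention the added covariate.

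The data come from Protocol 8.2.2, Table 5: "Optional] Assess items 6 and 7 of the TETRAS-PS serially across the day at 6 time points" at Baseline, and the same six at Week 8, where "time points should correspond to the same time of day as Baseline assessments". The first dose is taken at home the day after the Baseline Visit, so all six Baseline readings are undosed.

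The stratum term carries some severity information. SAP 5.1: "Randomization will be stratified by the TETRAS composite outcome score" (cut at 17) and by concomitant antitremor medication. By contrast, the primary MMRM in SAP 9.1.2 uses one baseline value per participant.

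**The concern.** A covariate that varies within a participant carries two different relations to the outcome. Between participants, a higher average baseline predicts a higher Week 8 score, and this is the severity adjustment one wants. Within a participant, a reading that happens to be high at one clock time predicts the same clock time at Week 8 only if the daily profile recurs. One common slope must serve both. The random participant effect absorbs differences between participants, so the fit leans towards the within-participant relation. If that relation is mostly noise, the slope on change is pulled towards −1 and the model comes close to analysing the raw Week 8 score.

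Precision is at stake in a small data set. Every other scheduled on-treatment TETRAS-PS rating is taken 1 hour after dosing. This is therefore the only planned analysis of measured tremor performance later in the dosing day, and it relies on participants who opt in.

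**Working it through.** **The plan's own figures.** There are none for this analysis: neither document gives power, a standard error, a sample size or variance components for the serial scores. The stated 90% power (80 per arm, difference 3.1, SD 6.0) reproduces at 90.5% but concerns the primary endpoint only.

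**Inputs.** From the documents: four arms at 1:1:1:1, six time points, the outcome and model terms above. Assumed, because the documents are silent:
- ICC, the between-participant share of the variance of one reading within a visit
- ρ, the correlation of a participant's underlying level between Baseline and Week 8
- r, the correlation between same-clock-time deviations at the two visits

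**Step 1: what the common slope estimates.** Set the variance of one reading to 1 at both visits. Regressing change on baseline with slope b − 1 is the same as regressing the Week 8 score on baseline with slope b.
- Within-participant slope: r.
- Between-participant slope: b_B = [ICC·ρ + r(1−ICC)/6] / v, with v = ICC + (1−ICC)/6.
- Common slope: b = (I_W·r + I_B·b_B)/(I_W + I_B), with I_W = 5(1−ICC)/σ² and I_B = 6v/(6τ² + σ²).
- Residual variances: σ² = (1−ICC)(1 + b² − 2br) and τ² = ICC(1 + b² − 2bρ).

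Severity left unadjusted enters τ² and lowers the weight on the between-participant relation, so the equations are solved by iteration.

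**Step 2: a worked case without the stratum** (ICC 0.8, ρ 0.85, r 0).
- v = 0.8 + 0.2/6 = 0.833, and b_B = 0.68/0.833 = 0.816.
- The solution is b = 0.178, with σ² = 0.206, τ² = 0.584, I_W = 1.0/0.206 = 4.85 and I_B = 5/(3.504 + 0.206) = 1.35. Check: 1.35 × 0.816/(4.85 + 1.35) = 0.178.
- About 0.178/0.816 = 22% of the between-participant slope survives.
- Variance behind a contrast at one time point: as written, 0.584 + 0.206 = 0.790. With mean plus deviation, (0.8 − 0.816² × 0.833) + 0.2 = 0.445. With no baseline covariate, 2 × 0.8 × 0.15 + 2 × 0.2 = 0.640.
- SE ratio against the split: √(0.790/0.445) = 1.33. Against no covariate: √(0.790/0.640) = 1.11.
- A contrast between time points depends only on σ²: √(0.206/0.200) = 1.01.

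**Step 3: simulation with the stratum.** Random-intercept REML fits, mainly 50 per arm, 100 to 600 replicates per scenario, with a medication stratum and a severity stratum (assumed correlation 0.6 with the underlying level). SE ratios are for a dose-versus-placebo contrast at one time point.

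| ICC | ρ | r | As written / split | As written / no covariate |
|---|---|---|---|---|
| 0.8 | 0.85 | 0 | 1.28 | 1.07–1.08 |
| 0.9 | 0.70 | 0 | 1.19 | 1.05 |
| 0.9 | 0.85 | 0 | 1.38 (empirical 1.37) | 1.21 |
| 0.95 | 0.95 | 0 | 1.89 | 1.66 |
| 0.8 | 0.70 | 0.3 | 1.05 | 0.94 |
| 0.8 | 0.85 | 0.3 | 1.12 | 1.00 |
| 0.8 | 0.70 | 0.5 | 1.01 | 0.93 |
| 0.8 | 0.85 | 0.5 | 1.05 | 0.98 |
| 0.8 | 0.70 | 0.7 | 1.00 | 0.93 |
| 0.8 | 0.85 | 0.7 | 1.01 | 0.97 |

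- At ICC 0.8, ρ 0.7, r 0 the ratio to the split is 1.15. Over all r = 0 scenarios it runs from 1.04 to 1.89. With scores rounded to the 0–9 scale it was 1.11 to 1.34.
- The fitted slope on the Week 8 scale at r = 0 is 0.06 to 0.22, against between-participant slopes of 0.44 to 0.94.
- For the effect averaged over the six times at r = 0 the ratio is 1.07 to 2.13.
- For the effect at 1 h minus the effect at 8 h it is 1.00 to 1.03 throughout.
- No material bias appeared, and model-based and empirical standard errors largely agreed.

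An SE ratio of 1.15 is equivalent to losing 1 − 1/1.15² = 24% of participants; a ratio of 1.37, to losing 1 − 1/1.37² = 47%.

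**The case against.** The strongest defence is that r may well be above zero by design. Readings are matched to the clock, antitremor medication must be stable (Inclusion Criterion 7), and caffeine and tobacco follow the participant's usual schedule on clinic days (Protocol 5.3.2). Each could make a personal daily profile recur, and a time-matched baseline is then a sensible covariate. This stands: at r of 0.7 or more there is nothing to gain. Against it, the score is a coarse sum of three readings, each collapsed to four levels, so small rating fluctuations can move it by a point. That makes a low r a reasonable worry, but the documents do not settle it.

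Four stronger readings are tempting and are not supported.
- A reader might infer that every treatment contrast is degraded. Contrasts between time points, which ask whether the effect changes over the day, are within-participant and essentially untouched.
- A reader might infer that about half the information is always lost. An SE ratio of 1.43 to 1.46 (1 − 1/1.43² = 51%) arises when visit-to-visit noise is placed at Week 8 only and the stratum is left out, but the stratum is in the planned model. In one set-up with equal noise at both visits the ratio was 1.17. It was 1.12 with the stratum added, and 1.04 if half of the within-day variance also recurs.
- A reader might infer that having no baseline covariate would be better. That depends on the assumptions: the ratio runs from 0.91 (rounded scores, ICC 0.7, ρ 0.7) to 1.66.
- A reader might infer biased estimates or invalid tests. Neither was seen.

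**Conclusion.** The point holds as a conditional loss of efficiency. With the stratum in the model, the SE of a dose-versus-placebo contrast at one time point is roughly 15–37% larger than under the split in mid-range scenarios when daily deviations do not recur at Week 8, and 4–89% larger over the wider range. It is about 1–12% larger at r of 0.3 to 0.5 (ICC 0.8) and about equal at 0.7 or more. All of this rests on assumed ICC, ρ and r.

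Priority is low. The serial assessments are optional, the endpoint is exploratory and outside type I error control, and the primary and key secondary analyses are unaffected. It is still worth correcting, because the split was the most precise model, or within about 2% of it, in nearly all scenarios and removes the dependence on an unknown r.

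**What to change.** In SAP 9.3.3, replace the single time-matched baseline term with two covariates: (1) the participant's mean Baseline sum of modified items 6 and 7 over the available serial Baseline readings, and (2) the time-matched deviation from that mean. Keep all other terms. Replacing the covariate by the mean alone is not a reliable substitute: at r = 0 the as-written model's SE was 0.88 to 1.67 times that of the mean-only model.

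Cost: one sentence in the SAP, one derived variable from data already collected, and one extra degree of freedom. A rule is also needed for participants with missing Baseline readings, for example using the mean of those available, accepting that a mean of fewer readings is noisier. Recording the baseline terms in SAP 7.6 would also make the departure from Protocol 9.4.4 visible.

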10. SAFETY

All safety analyses, summaries, listings and figures will use the Safety Analysis Set unless otherwise specified.

10.1. Exposure

10.1.1. Extent of Exposure

The duration of exposure will be derived as date of last dose of study intervention – date of first dose of study intervention + 1. Dosing Interruptions are not taken into account for the duration of exposure. The duration of exposure will be summarized using descriptive statistics. by treatment groups. Exposure summaries are based on data collected by the study intervention administration eCRF and data collected in IRT.

10.1.2. Treatment Compliance

Summary statistics for compliance to study intervention will be presented using descriptive statistics as well as counts and percentages, as appropriate, based on the Safety Analysis Set overall and by treatment group. Compliance will also be summarized by category (<75%, 75-125% and >125%). A listing of compliance will also be presented.

Compliance will be calculated as the number of capsules taken (i.e. total dispensed – total returned) divided by the number of capsules that should have been taken by the subject during that study period, expressed as a percentage i.e.

$$compliance(\%) = \frac{number\ of\ capsules\ dispensed-number\ of\ capsules\ returned}{number\ of\ capsules\ expected\ according\ to\ protocol}$$

10.2. Adverse Events

Adverse events (AEs) occurring from the first dose until the final study visit will be reported. If the Investigator becomes aware of a SAE within 14 days after the last dose of study intervention, the event must also be reported. In addition, any SAE assessed as related to study intervention or procedure by the Investigator must be reported regardless of time after study termination.

AEs will be coded to system organ class (SOC) and preferred term using the Medical Dictionary for Regulatory Activities (MedDRA), Version 27.0. The investigator will assess the relationship of each AE to study intervention. AE with a missing relationship to study intervention will be reported as related in the summaries. Severity, as determined by the Investigator, will be classed as mild, moderate, severe, life-threatening or fatal. AE with missing severity will be reported as missing in the summaries.

Note that participants who acquire COVID-19 or report AEs due to the COVID-19 public health emergency (e.g., anxiety) while on study will be coded accordingly and included in the adverse event summaries.

A treatment-emergent adverse event (TEAE) is defined as any event with onset date on or after the first dose of study intervention, including adverse events that occur until 14 days after the last dose date. For the purpose of calculating treatment emergence, incomplete onset dates will be imputed as detailed in Appendix 1: Date Imputation Rules.

Time of first onset of AE is calculated as: TEAE start date – First dose date + 1 and is categorized as:

- Week 1 ($1 \le \text{day of first onset of AE} \le 7$)
- Week 2 ($8 \le \text{day of first onset of AE} \le 14$)
- Week 3 (15 \leq day of first onset of AE \leq 21)
- Week 4 ($22 \le \text{day of first onset of AE} \le 28$)
- Weeks 5 to 8 (29 \leq day of first onset of AE \leq 56)
- Weeks 9 to 12 (57 \leq day of first onset of AE \leq 84)
- After Week 12 (84 < day of first onset of AE)

Only TEAEs are included in summary tables unless otherwise specified. If a subject has multiple episodes of events coded to the same SOC or PT, then the subject will be counted just once in the summaries for that term. Subject incidence of TEAEs by SOC and PT tables are sorted by SOCs (alphabetical order) and then by PTs (descending order) within each SOC for the overall frequency. For summaries by PT only, PTs will be sorted in descending order of overall frequency.

Each TEAE will be summarized by treatment group.

A general overall summary of TEAEs with the number and percent of participants who experienced the following types of events will be provided:

- Participants with any TEAE
- Participants with any related TEAE
- Participants with any serious TEAE
- Participants with TEAE by severity
- Participants with an AE outcome as death
- Participants with any TEAE leading to study intervention discontinuation
- Any TEAE leading to study intervention dose reduction
- Any TEAE leading to study intervention dose interruption
- Any TEAE not recovered

Subject incidence of TEAEs tables will be summarized by the following:

- SOC and PT
- TEAE reported ≥5% in any treatment group by SOC and PT
- PT only
- TEAE reported >=5% in any treatment group by PT
- Maximum severity by SOC and PT
- Treatment-related by SOC and PT
- TEAEs of special interest by category (defined in Section 10.2.1) and PT

- TEAEs leading to permanent withdrawal of study intervention by SOC and PT
- TEAEs leading to dose reduction of study intervention by SOC and PT
- TEAEs leading to dose interruption of study intervention by SOC and PT
- TEAE by Time of First Onset, SOC, and PT
- Serious TEAE by Time of First Onset, SOC, and PT
- Serious treatment related TEAE by Time of First Onset, SOC, and PT

Separate adverse event listings will be provided including the following:

- All adverse events
- Adverse events with an outcome of death
- Adverse events leading to permanent withdrawal of study intervention
- Serious adverse events
- Adverse events of special interest, defined in defined in Section 10.2.1

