Type of Design	Randomized, parallel-group, 4-arm, multicenter
	Randomization will be stratified by the following:
	 The select modified items from the TETRAS-ADL subscale and TETRAS-PS (ie, TETRAS composite outcome score)^a (≤ 17 or > 17), as assessed at the Baseline Visit
	The use of concomitant antitremor medication (Yes or No)
Type of Control	Placebo Control
Study Blinding	Double-blind (Interactive response technology [IRT])
Population	Participants with moderate to severe ET
Number of Participants	Approximately 400 participants will be randomized, with approximately 100 participants randomized to each treatment arm and 80 evaluable participants in each treatment arm of the study.
Duration of Participation	The study starts from the time participants sign the informed consent form (ICF) through the end of the study procedures/contact. The study comprises 3 periods: up to 35 days Screening Period (an additional 28 days are permitted for participants who require washout of primidone) including Baseline, followed by a 12-week Doubleblind Treatment Period, and a 2-week Safety Follow-up Period. Each participant will be enrolled for approximately 19 weeks.
Number of Treatment Arms	4
Treatment Groups	10, 20, or 30 mg/day JZP385, or placebo
Data Monitoring Committee	Not applicable

^a The TETRAS composite outcome score is the sum of modified items 1 to 11 of the TETRAS-ADL subscale and modified items 6 and 7 of the TETRAS-PS. For TETRAS-ADL, each item is modified from 5 response items to 4 response items by collapsing options 0 and 1 together and for TETRAS-PS, each item is modified from 9 response items (due to 0.5 scoring increments) to 4 response items.

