8.3.6. Suicidal Ideation and Behavior Risk Monitoring

JZP385 is considered to be a central nervous system-active study intervention. Participants being treated with JZP385 should be monitored appropriately and observed closely for suicidal ideation and behavior or any other unusual changes in behavior, especially at the beginning and end of the course of study intervention, or at the time of dose changes, either increases or decreases. Participants who experience signs of suicidal ideation or behavior, should undergo a risk assessment. All factors contributing to suicidal ideation or behavior should be evaluated and consideration should be given to discontinuation of the study intervention.

Baseline assessment of suicidal ideation and behavior/ intervention emergent suicidal ideation and behavior will be monitored using the C-SSRS. At the Screening Visit, the Baseline/Screening Version of the C-SSRS will be administered to participants to exclude any individuals with active suicidal ideation or behavior.

The Since Last Visit Version of the C-SSRS will be administered to participants at every clinic visit after their Screening visit, including the Baseline and Follow-up visits. At the Baseline Visit, any participant who reports active suicidal ideation (eg, a positive response to Question 4

or 5 on the C-SSRS) or behavior (eg, a positive response to any suicidal behavior question on the C-SSRS) will be excluded. At post-baseline visits, active suicidal ideation or behavior must be recorded as an AE and reported to the sponsor or designee within 24 hours of first knowledge of the event by study personnel. Please refer to Appendix 4 for details on reporting other reportable experiences (OREs).

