9.4.5. Safety Analysis

All safety analyses will be performed on the Safety Population. Safety analyses will be descriptive; no formal statistical testing will be performed.

Adverse Event Analyses:

Adverse events will be mapped to system organ classes and preferred terms using the Medical Dictionary for Regulatory Activities (MedDRA). The participant incidence of AEs, AEs related to study intervention, SAEs, AEs leading to discontinuation, and fatal AEs will be summarized. This overall summary will also provide AEs by maximum severity.

The participant incidence of AEs, AEs related to study intervention, AEs, and AEs leading to discontinuation will also be presented by SOC and preferred term. Preferred term summaries may also be provided.

The participant incidence of an AE will be summarized; if a participant has multiple events with the same PT occurring in different periods, the event will be reported for each of those periods. Multiple increases in severity will only be counted as one AE.

Vital Signs:

For each vital sign parameter, summary statistics will be provided for observed and change from baseline values by scheduled visit.

Protocol JZP385-201-04 Amendment 04

Physical Examinations

Observed and change from baseline values for weight will be summarized descriptively by scheduled visit.

12-lead ECG

Observed and change from baseline values for ECG intervals will be summarized descriptively. QT abnormalities will be assessed; the number and percent of participants with values or change from baseline values exceeding certain thresholds will be tabulated.

Laboratory Evaluations

Observed and change from baseline laboratory evaluations will be summarized descriptively.

C-SSRS

Columbia Suicide Severity Rating Scale parameters will be summarized by scheduled visit.

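### The SAP counts each adverse event term once over treatment plus the 14 days after it, without recording that this drops the protocol's per-period rule; events starting after the last dose are only partly visible in the tables

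*SAP*

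**What the plan says.** **Protocol.** Table 3 of the Synopsis (1.1) describes screening "followed by a 12-week Doubleblind Treatment Period, and a 2-week Safety Follow-up Period". Section 9.4.5, on the incidence of adverse events, states: "if a participant has multiple events with the same PT occurring in different periods, the event will be reported for each of those periods". It does not define periods for the adverse event tables. Section 8.3.6 calls JZP385 a CNS-active agent and asks for close observation for suicidality or other unusual changes in behaviour, "especially at the beginning and end of the course of study intervention".

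**SAP.** Section 10.2 uses one treatment-emergent window, starting at the first dose and "including adverse events that occur until 14 days after the last dose date". Only TEAEs enter the summary tables unless otherwise specified. The counting rule is: "If a subject has multiple episodes of events coded to the same SOC or PT, then the subject will be counted just once". Of the 13 incidence tables listed, none is split at the last dose date. The nearest is "TEAE by Time of First Onset, SOC, and PT", with versions for serious and for serious related TEAEs. Its last category is "After Week 12 (84 < day of first onset of AE", where the day is counted from the first dose.

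SAP 7.6 lists three changes to planned analyses: item-level imputation, mITT to ITT, and removal of presyncope from the events of special interest. The per-period counting rule is not mentioned.

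**The concern.** A stated protocol rule has been replaced by a different one without being recorded, and the replacement removes information. For a CNS-active drug, a safety reader will want to know whether events begin or return once dosing stops, and whether that differs between arms. Tables that run treatment and follow-up together, counting each term once, answer this only in part.

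The gap affects two groups of events. One is the off-drug events of participants who stop early, which fall into calendar rows filled mainly by other participants' on-drug time. The other is terms that appear on drug and recur after stopping. Protocol 4.2 says that in the earlier phase 2 study events were reported primarily in the first week and that most of the common ones resolved within a week of onset. Protocol 2.3.1 names dizziness, headache, euphoric mood and insomnia as the common events in ET. If such an event occurs in Week 1 and returns after the last dose, a first-onset table shows only Week 1.

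**Working it through.** The plan states no figure on this point, so the check is a comparison of rules plus day counts.

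**Inputs**
- TEAE tail: 14 days after the last dose (SAP 10.2).
- Start of the After Week 12 row: Day 85, counted from the first dose (SAP 10.2).
- Week 12 visit: Day 84 ± 3, with a dose taken in clinic (Protocol 1.3 and 6.4).
- Follow-up of early stoppers: 2 weeks after the early discontinuation visit (Protocol 1.3, footnote d).
- Planned dropout: 20%, or 20 of 100 per arm (Protocol 9.2).
- Steady state reached in 5 days (Protocol 4.3).

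**Rules side by side.** Take a participant with dizziness on Day 3, resolved, and again 4 days after the last dose. If the periods are Double-blind Treatment and Safety Follow-up, Protocol 9.4.5 reports the term in both. SAP 10.2 counts the participant once, and the first-onset table places that count in Week 1.

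**Step 1: where off-drug days fall.** Let L be the last dose day.
- Off-drug share of the TEAE window = 14 / (L + 14).
- Off-drug days reaching the After Week 12 row = max(0, min(14, L + 14 − 84)).

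| L | Off-drug share | Off-drug days in After Week 12 |
|---|---|---|
| 7 | 14/21 = 67% | 0 of 14 |
| 14 | 14/28 = 50% | 0 of 14 |
| 28 | 14/42 = 33% | 0 of 14 |
| 70 | 14/84 = 17% | 0 of 14 |
| 77 | 14/91 = 15% | 7 of 14 |
| 84 | 14/98 = 14% | 14 of 14 |

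**Step 2: completers at the edges of the visit window.** A last dose on Day 81 leaves 84 − 81 = 3 off-drug days in the Weeks 9 to 12 row. A last dose on Day 87 puts 87 − 84 = 3 on-drug days into After Week 12. For completers the row is therefore accurate to within 3 days.

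**Step 3: per arm.** With 14 days of follow-up for all 100 participants, off-drug time is 100 × 14 = 1,400 person-days. If 20 participants all stop by Day 70, 20 × 14 = 280 of these (280/1,400 = 20%) lie in rows up to Week 12. The other 80% are in or close to the After Week 12 row.

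**Step 4: how drug-free the tail is.** The documents give no half-life. Reading 5 days to steady state as 4 to 5 half-lives gives an assumed half-life of 1.0 to 1.25 days. The fraction left after d days is 0.5^(d / half-life). At 5 days it is 0.5^5 = 3% to 0.5^4 = 6%, and at 14 days it is below 0.1%. On that assumption roughly the last 9 of the 14 days are nearly drug-free and the first few are not. This covers the parent drug only; Protocol 2.2 mentions two active metabolites, to which the assumption may not apply.

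**The case against.** The strongest reply is that most post-drug information is already planned. Completers are about 80 of 100 per arm, and their first post-drug onsets appear in the After Week 12 row. All adverse events are listed, so a recurrence can be found case by case. Suicidality, the main subject of Protocol 8.3.6, has its own instrument, given up to the Safety Follow-up visit and summarized by visit and arm. Safety analyses are descriptive, so no test or estimand is affected. All of this stands, and it rules out two stronger readings that a reader might infer.

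- *Post-drug events cannot be seen at all.* The documents do not support this, because of the After Week 12 row, the listing and the C-SSRS summaries.
- *The SAP counts off-drug events as on-treatment.* It does not. Its label is treatment-emergent and its rows are days since the first dose. The protocol sets no TEAE window in days, so the 14-day tail contradicts nothing.

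It is also fair to say that Protocol 9.4.5 leaves periods undefined. Reading them as Double-blind Treatment and Safety Follow-up is an inference, though a natural one: these are the named periods in Protocol Table 3, and SAP Table 5 uses the same two in its study period column. On any other reading, the SAP still has no per-period counting of a repeated term.

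The reply does not remove three things: the unrecorded departure, the misplacement of early stoppers' off-drug events, and the loss of recurrences from the tables. A listing allows case review but does not give a comparison between arms.

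**Conclusion.** The point holds as an unrecorded departure from Protocol 9.4.5 and as a partial gap in the safety tables. The TEAE definition itself is not in error.

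The gap is about 20% of off-drug person-days per arm, if the planned 20% dropout means stopping study drug, all of it happens by Day 70, and all are followed for 14 days. Later stopping makes it smaller. Recurrences after stopping are missing from the first-onset tables for completers as well, and the documents do not allow that number to be estimated. The shares of 14% to 67% in Step 1 are shares of calendar days for chosen stopping dates and say nothing about event risk.

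A reader might also infer that the drug has a withdrawal effect, or that the higher-dose arms carry more off-drug time. The documents report no withdrawal syndrome and give no stopping rates by dose, so both remain open possibilities that a split table would help to examine. Alpha, power and the estimands are unaffected.

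**What to change.** In SAP 10.2, keep the TEAE definition and the overall tables. Add a descriptive TEAE table by SOC and PT split at each participant's last dose date (on or before, versus after), with the same split for serious TEAEs and for adverse events of special interest. Count a participant once per PT per period, as Protocol 9.4.5 states, and use participants observed in that period as the denominator. State that these are the periods meant in Protocol 9.4.5.

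Add a note that the first days after the last dose still include residual drug. Add another that the two periods differ in length, so the useful comparison is between arms within a period.

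Record the counting rule for the overall tables in SAP 7.6. If the sponsor prefers not to add the tables, that entry with its reason is the minimum.

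The cost is one derived flag and two or three extra tables, with no new data. The period denominators and the split for serious and special-interest events go beyond what Protocol 9.4.5 requires; they are recommended because they make the tables interpretable.
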